4 STUDY DESIGN

4.1 Design

Overview

The trial is a phase 1a/1b study is a randomized, observer-blind, placebo-controlled.

Description of study parts and groups

A schematic of the study design is shown in Figure 1.

Phase 1a

60 healthy adults, age 18-54 years of age with no previous clinical or laboratory diagnosis of COVID-19 or SARS-CoV-2 infection and not previously received an experimental or authorized COVID-19 vaccine will be enrolled into the Phase 1a part of the study to evaluate the safety, tolerability and immunogenicity of a one-dose or two-dose regimen of VBI-2902a at a dose level of 5 µg of S protein or placebo. Participants will be randomized at a 2:1 ratio to VBI-2902a or placebo:

- **Group G1** – 20 participants will receive VBI-2902a at a dose of 5 µg of S protein at Day 1 and placebo at Day 28.
- **Group G2** – 20 participants will receive VBI-2902a at a dose of 5 µg of S protein at Days 1 and 28.
- **Group G3** – 20 participants will receive placebo at Days 1 and 28.

An Independent Data Safety Monitoring Board (DSMB) will review blinded safety data (reactogenicity, adverse events (AEs) and safety laboratory assessments) at Day 7 after the first vaccination. The second vaccination will only be given if the DSMB confirms that Day 7 safety is acceptable and that stopping rules were not met. The DSMB will further review blinded post-vaccination safety through Day 35, 7 days after the second vaccination and through Day 56, 28 days after the second vaccination. A Study Steering Committee (SSC), comprised of representatives from the study sponsor (not involved in study operations) and external vaccine experts, will review unblinded immunogenicity data 7 days and 28 days after the second vaccination. The study will be unblinded following DSMB review of safety data collected through Day 56.

Phase 1b

A total of 54 healthy adults, age 18-54 years, with no history of clinical or laboratory diagnosis of SARS-CoV-2 infection or COVID-19 illness, will be enrolled in the Phase 1b part of the study.

Participants who had been previously vaccinated with authorized mRNA COVID-19 vaccine(s) will be randomized at a 1:1 ratio to receive, in a blinded fashion, one dose of VBI-2905a or placebo:

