On the vaccination visits, participants will remain at the site for at least 60 minutes for an evaluation of AEs and vital signs. Participants will be contacted by phone 3 days after each vaccination for a safety follow up call. Diary cards will be distributed to study participants at vaccination visits to record body temperature, local and systemic reactions from day of the vaccination(s) and the next 6 days. Serious AEs (SAEs) and medically-attended AEs (MAAEs) will be recorded throughout the study.

In Phase 1a, participants will visit the study site for dose administration, safety assessments and blood sample collection on Days 1 and 28 (prior to study vaccination) and for safety assessments and blood sample collection on Days 7, 35, 56, 112, 224 and 336.

In Phase 1b, participants will visit the study site for dose administration, safety assessments and blood sample collection on Day 1 for safety assessments and blood sample collection on Days 7, 14, 28, 56, 84, 168 and 336. Study participants will be tested for SARS-CoV-2 infection by PCR or rapid antigen test and surveilled for signs and symptoms of COVID-19 illness throughout the study. Duplicate nasopharyngeal swab samples will be retained for storage and potential sequencing of viral RNA should samples test positive for SARS-CoV-2 infection.

Participants will be followed until the study completion on Day 336. If a subject is lost to follow-up, every effort will be made by the study center personnel to contact the subject and to determine the reason for discontinuation. Measures taken to follow-up will be documented.

Figure 1: Clinical Trial Design

* Not previously vaccinated with any licensed or experimental COVID-19 vaccine and no history of clinical or laboratory diagnosis of SARS-CoV-2 infection or COVID-19 illness

** Received a full course of an authorized mRNA COVID-19 vaccine at least 4 months prior to the study and no history of clinical or laboratory diagnosis of SARS-CoV-2 infection or COVID-19 illness

Table 1: Phase 1a Schedule of Events

Schedule of Events	Screening								Study Period	End-of Study Early D/C	
	1	2	Phone Call	3	4	Phone Call	5	6	7	8	9
Visit											
Study Day	-28 to -1	1	3	7	28	31	35	56	112	224	336
Study Month (28 days)	<-1	0	0.1	0.25	1	1.1	1.25	2	4	8	12
Visit Intervals (Days)	n/a	n/a	±1	+3	±3	±1	±3	±3	±7	±14	±14
Informed consent	●	●									
Inclusion/exclusion criteria	●										
Confirm ongoing eligibility		●									
Demographics	●	●	●								

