3 STUDY DESIGN

Overview

The trial will be a phase 1a/1b study, randomized, observer-blind, placebo-controlled.

Description of study parts and groups

Phase 1a

Phase 1a of the study will evaluate the safety, tolerability and immunogenicity of a one-dose or two-dose regimen of the VBI-2902a at the low dose level of 5 µg of S protein or placebo in 60 healthy adults 18 to 54 years of age with no previous clinical or laboratory diagnosis of COVID-19 or SARS-CoV-2 infection and not previously received an experimental or authorized COVID-19 vaccine. Participants will be randomized to three cohorts at a 1:1:1 ratio (2:1 ratio to VBI-2902a or placebo [saline]):

- **Group G1** – 20 participants will receive VBI-2902a at a dose of 5 µg of S protein at Day 1 and placebo at Day 28.

- **Group G2** – 20 participants will receive VBI-2902a at a dose of 5 µg of S protein at Days 1 and 28.
- **Group G3** – 20 participants will receive placebo at Days 1 and 28.

An Independent Data Safety Monitoring Board (DSMB) will review blinded safety data (reactogenicity, adverse events and safety laboratory assessments) at Day 7 after the first vaccination. The second vaccination will only be given if the DSMB confirms that Day 7 safety is acceptable and that stopping rules were not met. The DSMB will further review blinded post-vaccination safety through Day 35, 7 days after the second vaccination and through Day 56, 28 days after the second vaccination. A Study Steering Committee (SSC), comprised of representatives from the study sponsor (not involved in study operations) and external vaccine experts, will review unblinded immunogenicity data 7 days and 28 days after the second vaccination. The study will be unblinded following DSMB review of safety data collected through Day 56.

Phase 1b

Phase 1b of the study will evaluate the safety, tolerability and immunogenicity of a one-dose regimen of VBI-2905a at a 5 µg dose level of S protein in healthy adults (18-54 years) who had been previously vaccinated with mRNA vaccines.

The DSMB will perform an early review of blinded post-vaccination safety data at Day 7 (reactogenicity, AEs and safety laboratory assessments). DSMB will review blinded Day 7 safety data after the first 10 participants in groups G4 and G5 (previously vaccinated). Only after the DSMB confirms that safety is acceptable and that stopping rules were not met will the enrollment in the respective study groups continue to its completion.

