5 STATISTICAL CONSIDERATIONS AND ANALYSIS

5.1 General Guidance on Data Presentation

Unless otherwise specified, continuous variables will be summarized using descriptive statistics, including n, mean, standard deviation (SD), median, Q1 (1st Quartile), Q3 (3rd Quartile), min and max. Count variables will be summarized using frequency and percentage.

Min and max will have same decimal place as raw data; mean, median, Q1, and Q3 will have one additional decimal place; SD will have two additional decimal places. Percentage, and CV (Coefficient of Variation) (if presented), will be rounded to one decimal place.

For all statistical analyses, unless explicitly stated otherwise, percentages will utilize a denominator corresponding to the number of subjects within each treatment groups.

All summary tables will be presented by treatment groups. Listings will be presented to for all data collected in the CRF.

Generally, the DSMB outputs will be presented using actual treatment for the SC and will summarize the date from each study phase and treatment group separately. The DSMB will review blinded safety data and displays (reactogenicity, AEs and safety laboratory assessments) for treatment/age groupings within phases 1a and 1b. That being said, if deemed necessary, individual subjects may be unblinded per DSMB request. During Phase 1b of the study, the DSMB will review unblinded safety data and displays (reactogenicity, AEs and safety laboratory assessments). Details are outlined in the DSMB SAP.

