6.3.1.2 AE Summaries

An overview summary of TEAEs including:

- 1) Counts and percentages of subjects
 - a. With any TEAE,
 - b. With any local solicited AEs during 7 days of vaccination dosing,
 - c. With any systemic solicited AEs during 7 days of vaccination dosing,
 - d. With any unsolicited AEs within 28 days of each vaccination dose,
 - e. With any unsolicited MAAEs at Day 56 and 28 days after each vaccination dose,
 - f. With any unsolicited SAEs at Day 56 and 28 days after vaccination dose,
 - g. With any unsolicited AEs leading to discontinuation of study vaccination,
 - h. With any unsolicited AEs leading to study discontinuation,
 - i. With any unsolicited AEs during the study,

j. With any unsolicited SAEs during the study.
will be presented stratified by treatment and age group.

For each type of AE noted in the overall summary point 2 except solicited AEs (2b and 2c), we will additionally produce summaries of the AEs by SOC and PT. Furthermore, summaries of event types 2d, and 2i will be presented for by SOC, PT, and severity (mild/moderate/severe/potentially life threatening).

Solicited AEs will be summarized separately for local AEs, systemic AEs, and fever >38 centigrade as collected on the solicited AEs eCRF pages. These summaries will be presented for each dose separately and cumulatively, will count the number of subjects experiencing at least one solicited AE, and will count the number of subjects experiencing at least one of each of the solicited AEs ordered per the solicited AEs eCRF pages.

Lastly, within the solicited AE by SOC/PT summary, 2-sided, alpha=0.05 Fisher's Exact tests will be performed to assess differences in rates of these adverse events between the treatment groups. No adjustment will be made to account for multiplicity of tests performed.

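### G1 and G2 are treated identically until the Day 28 injection, but the SAP text plans no pooled first-dose analysis, so each first-dose contrast with placebo leaves a quarter of the available information unused.

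*SAP*

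**What the plan says.** **Design.** SAP section 3 gives three Phase 1a groups: "Participants will be randomized to three cohorts at a 1:1:1 ratio". G1 receives 5 µg VBI-2902a "of S protein at Day 1 and placebo at Day 28", and G2 receives the same dose level "of S protein at Days 1 and 28". For G3, "20 participants will receive placebo at Days 1 and 28". Protocol 4.1 describes G1 in the same way ("S protein at Day 1 and placebo at Day 28"). Its account of the Phase 1a visits puts dosing, safety assessment and blood sampling on "Days 1 and 28 (prior to study vaccination"), so the Day 28 sample still follows only one dose in both active groups.

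**Analysis.** SAP 5.1: "All summary tables will be presented by treatment groups". SAP 6.3.1.2 stratifies the adverse event overview by treatment and age group. It splits the solicited events by dose ("These summaries will be presented for each dose separately and cumulatively") and runs unadjusted two-sided Fisher tests between treatment groups. SAP 6.4.2 takes GMT intervals within each group. The only day written into its fold-rise model is Day 56.

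**Protocol totals.** Protocol 4.4 evaluates safety and tolerability over about 67 recipients of either vaccine and about 47 placebo recipients. It also uses safety, tolerability and four-fold antibody rises at Days 28 and 56 to decide on the one-dose regimen.

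**The concern.** Up to the second injection, G1 and G2 are two random samples given the same product at the same dose under the same blind. First-dose reactions and Day 7 and Day 28 titers therefore estimate one quantity in 40 participants, against 20 on placebo. The SAP text describes two separate comparisons of 20 with 20.

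Safety and tolerability form the primary objective, and solicited events within 7 days of each vaccination are a primary endpoint. The cost falls on how tightly first-dose rates are bounded and how well a difference from placebo can be seen. It also affects the one-dose decision, because at Day 28 G2 says as much about a single dose as G1 does.

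**Working it through.** **Inputs.** Group sizes are 20, 20 and 20 (SAP 3). The target is a two-fold titer difference, which is log10(2) = 0.301, with 80% power and alpha 0.05 (SAP 3.3). The documents give no SD of log10 titer, so 0.3 to 0.6 is assumed. They give no expected event rates, so those below are also assumed.

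**1. The plan's own figures.** The safety totals reproduce: 20 + 20 + 27 = 67 active and 20 + 27 = 47 placebo. The 80% power cannot be confirmed without an SD. At 20 per group, two-sided, it requires

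SD = 0.301 / [√(2/20) × (1.960 + 0.842)] = 0.34 by the normal approximation, or 0.33 by the t distribution.

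**2. Precision of a first-dose contrast with placebo** (variance in units of SD²).

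- By group: 1/20 + 1/20 = 0.100
- Pooled: 1/40 + 1/20 = 0.075
- Information kept by one unpooled contrast: 0.075/0.100 = 75%
- Standard error ratio: √0.75 = 0.866, so 13% smaller with pooling
- Active arm alone: √(20/40) = 0.707, so 29% smaller

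**3. Rare events after dose 1.**

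- Zero events, exact two-sided 95% upper limit, 1 − 0.025^(1/n): 16.8% at n = 20 and 8.8% at n = 40
- Chance of at least one event at a true 5% rate, 1 − 0.95^n: 64% at n = 20 and 87% at n = 40

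**4. Fisher power.** This is exact: binomial probabilities are summed over all tables with two-sided p ≤ 0.05.

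| Assumed active v placebo rate | 20 v 20 | 40 v 20 |
|---|---|---|
| 50% v 20% | 0.41 | 0.57 |
| 60% v 20% | 0.65 | 0.81 |
| 40% v 10% | 0.49 | 0.67 |

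**5. Power for a two-fold titer difference.** This uses the noncentral t with noncentrality 0.301 / [SD × √(1/n1 + 1/n2)] and n1 + n2 − 2 degrees of freedom, two-sided 0.05.

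| Assumed log10 SD | 20 v 20 | 40 v 20 |
|---|---|---|
| 0.3 | 87% | 95% |
| 0.33 (implied by the plan's 80%) | 80% | 91% |
| 0.4 | 64% | 77% |
| 0.5 | 46% | 58% |
| 0.6 | 34% | 44% |

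**The case against.** A reader might infer that the SAP throws away half of the first-dose data. It does not. Every vaccinated participant is in the Safety Cohort, every group is tabulated and all events are listed. The by-dose layout of the solicited tables even lets a reader add the G1 and G2 counts. Half describes only the share of first-dose recipients in each active column; the loss in a contrast with placebo is a quarter.

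A reader might also infer that the trial's outputs never pool. That can be said only of the SAP text. The table templates are in a separate document (SAP 1), treatment group is not defined as regimen or product, and SAP 4.3 assigns by vaccination received. SAP 6.4.1 does speak of 5 µg and 10 µg dose groups, but the current design has no 10 µg group. The sentence also runs to Days 35 and 56, so it is not a first-dose pooling rule.

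Other points against carry some weight:

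- Protocol 4.4 itself names one-dose and two-dose groups at Days 7 and 28, so separate display follows the protocol. This supports keeping the columns, not omitting a pooled one.
- Protocol 10.3 calls immunogenicity exploratory, and the Day 56 fold-rise model must not pool. Both stand. The stronger case is first-dose safety.
- The Fisher tests are unadjusted and drive no stopping rule. The gain is in description and precision, not in a decision threshold.
- Adding a column is not enough for every table. The unsolicited and laboratory summaries use windows of 28 days after each vaccination and Day 56. With a second injection allowed at Day 28 ± 3, a dose-1 window can run past it.

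Adding counts by hand does not replace pre-specification. The tests and GMT contrasts would then be unplanned, and each phase is unblinded after the Day 56 safety review (Protocol 8.7.1).

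**Conclusion.** The point holds as a moderate gap in efficiency and reporting. G1 and G2 are interchangeable until the second injection, and the SAP text specifies no analysis that uses this, although Protocol 4.4 frames safety over combined totals. No planned estimate is biased and no objective becomes unanswerable.

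The 25%, 13% and 29% figures and the zero-event limits depend only on the planned group sizes. The Fisher gains rest on assumed event rates and the titer gains on an assumed SD. Across SDs of 0.3 to 0.6, the gain in power for a two-fold difference is 8 to 13 percentage points.

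**What to change.** Keep all by-group columns and add the following to the SAP:

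1. **Dose-1 solicited events:** a pooled G1+G2 column (n = 40) beside G3 (n = 20), with the Fisher test run as pooled v G3.
2. **Day 7 and pre-dose Day 28 immunogenicity:** a pooled column and contrast with G3 for GMT, fold rise and four-fold response.
3. **Unsolicited events and laboratory abnormalities:** a pooled first-dose summary cut off at each participant's actual second-injection date.
4. **Definition:** state for each table and test whether treatment group means regimen or product received.
5. **Limit:** keep G1 and G2 separate for all data after the second injection, including the Day 56 fold-rise model.

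Items 1 and 2 use data already collected and cost one column and one contrast in planned tables. Item 3 costs a few extra tables. No new participants, visits or samples are needed. If Phase 1a is already unblinded when the SAP is changed, label the pooled comparisons as added after unblinding.

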6.3.1.3 AE Listings

The following separate listings of AEs will be presented:

- All Unsolicited AEs
- All solicited AEs
- All SAEs
- All AEs leading to death
- All AEs leading to discontinuation of study vaccination
- All AEs leading to study discontinuation.

6.3.2 Clinical Laboratory Evaluation

6.3.2.1 Overall

An overall summary of laboratory abnormalities (hematology, biochemistry, and urinalysis) will be created for events taking place at Day 56 and 28 days after each study vaccination. This summary will present the counts and percentages of subjects experiencing each type and will further break down abnormalities by severity.

6.3.2.2 Hematology

A summary of hematology lab results for the absolute and change from baseline values will be presented by visit.

A listing for hematology results will be created together with the normal ranges and severity grades. Lab values that are below or above the normal ranges will be flagged.

6.3.2.3 Chemistry

Chemistry lab results will be presented in similar pattern to hematology.

6.3.2.4 Urinalysis

Urinalysis lab results will be presented in a similar pattern to hematology for all quantitative tests. For any qualitative tests being performed counts and percentages of normal vs. abnormal results will be presented.

6.3.2.5 SARS-CoV-2 Testing

Results of SARS-CoV-2 testing will be summarized using counts and percentages of positive vs. negative results by time point. COVID-19 symptom surveillance will also be summarized.

Clinical Criteria

In the absence of a more likely diagnosis, at least two of the following symptoms or signs:

- fever (measured or subjective)
- chills
- rigors
- myalgia
- headache
- sore throat
- nausea or vomiting
- diarrhea
- fatigue
- congestion or runny nose

Or any one of the following symptoms:

- cough
- shortness of breath
- difficulty breathing
- new olfactory disorder
- new taste disorder

Or severe respiratory illness with at least one of the following:

- Clinical or radiographic evidence of pneumonia
- Acute respiratory distress syndrome (ARDS)

6.3.3 Vital Signs

A summary of vital signs will be presented by visit & time point. Within each dosing visit, change from pre-dose vital signs will also be summarized. The counts of subjects presenting abnormal vital signs by visit and severity will be produced for fever >38 centigrade, tachycardia, bradycardia, and hypertension.

6.3.4 Physical Examinations

A full physical examination will be conducted at the screening visit and history-directed physical examinations may be completed at subsequent visits. A summary of these findings will be presented by visit and body system.

6.4 Immunogenicity Analyses

Unblinded Immunogenicity analyses will be provided at day 35 and day 56 analyses

Immunogenicity analysis will censor the immunogenicity measurements first time after the participants receive a licensed (non-study) COVID-19 vaccines or tested positive SARS-CoV-2 infection or develop COVID-19 illness during the study

